8.1. Discontinuation from Study Treatment

8.1.1. *Permanent Discontinuation from Study Treatment*

Following randomization, it is expected that patients will remain on study medication for the duration of the Treatment Period (through Visit 11). Patients will be required to permanently discontinue from study drug only in the following circumstances:

- if a patient is inadvertently enrolled and it is determined that continued treatment with study drug would not be medically appropriate (see Section 8.1.3)
- if a patient is diagnosed with an active or untreated malignancy (other than basal or squamous cell skin cancer, in situ carcinomas of the cervix, or in situ prostate cancer) after randomization
- if a patient is diagnosed by the investigator with acute or chronic pancreatitis
- if a patient is diagnosed with C-cell hyperplasia or MTC after randomization
- if a patient develops an eGFR <15 mL/min/1.73 m² (confirmed on retest) as calculated by CKD-EPI
- if the patient or the patient's designee, for example, legal guardian, requests that the patient be withdrawn from study drug
- if the investigator or sponsor decides that the patient should be withdrawn from study drug; if the investigator decides to permanently discontinue study treatment because of an SAE or a clinically significant laboratory value, Lilly or its designee should be alerted immediately
- if the sponsor decides that a treatment arm and patients in that arm should be withdrawn from study drug

Discontinuation of the investigational product for abnormal liver tests **should be considered** by the investigator when a patient meets 1 of the following conditions after consultation with the Lilly designated medical monitor:

- ALT or aspartate aminotransferase (AST) $>8 \times \text{ULN}$
- ALT or AST $>5 \times \text{ULN}$ for more than 2 weeks
- ALT or AST $>3 \times \text{ULN}$ and total bilirubin level $>2 \times \text{ULN}$ or prothrombin time $>1.5 \times \text{ULN}$
- ALT or AST $>3 \times \text{ULN}$ with the appearance of fatigue, nausea, vomiting, right upper quadrant pain or tenderness, fever, rash, and/or eosinophilia ($>5\%$)
- Alkaline phosphatase $>3 \times \text{ULN}$

- Alkaline phosphatase $>2.5\times\text{ULN}$ and total bilirubin $>2\times\text{ULN}$
- Alkaline phosphatase $>2.5\times\text{ULN}$ with the appearance of fatigue, nausea, vomiting, right quadrant pain or tenderness, fever, rash, and/or eosinophilia ($>5\%$)

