9.2.2.4. C-Cell Hyperplasia and C-Cell Neoplasms

Individuals with personal or family history of certain thyroid or nonthyroid endocrine abnormalities or certain preexisting laboratory and genetic characteristics will be excluded from the study (see Section 6.2). Patients with a personal or family history of MTC or personal history of multiple endocrine neoplasia syndrome type 2, or who have serum calcitonin ≥ 20 ng/L at study entry as determined by the central laboratory will be excluded. The assessment of thyroid safety during the trial will include reporting of thyroid treatment-emergent (TE) AEs (TEAEs) and measurements of calcitonin according to the Schedule of Activities (Section 2).

Patients who develop serum calcitonin increases $\geq 50\%$ of the screening value AND an absolute value ≥ 20 ng/L and < 35 ng/L at a postrandomization visit will be asked to repeat the measurement within 1 month. If this repeat value is increasing ($\geq 10\%$ increase from the initial elevated value), the patient will be encouraged to undergo additional endocrine assessment and longer-term follow-up by an endocrinologist to rule out a serious adverse effect on the gland.

Patients with an increase in serum calcitonin $\geq 50\%$ of the screening value AND an absolute value ≥ 35 ng/L at a postrandomization visit will be asked to immediately undergo additional endocrine assessments and longer-term follow-up by an endocrinologist.

For patients who require additional endocrine assessments due to increased calcitonin concentration per the criteria provided in this section or for thyroid-related TEAEs, data from the follow-up assessments will be collected on a specific eCRF.

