9.4.3.1. Hepatic Safety Monitoring

If a study patient experiences elevated ALT $\geq 3 \times \text{ULN}$, alkaline phosphatase $\geq 2 \times \text{ULN}$, or elevated total bilirubin $\geq 2 \times \text{ULN}$, liver testing ([Appendix 4](#)) should be repeated within 3 to 5 days including ALT, AST, alkaline phosphatase, total bilirubin, direct bilirubin, gamma-glutamyl transferase (GGT), and creatine kinase to confirm the abnormality and to determine if it is increasing or decreasing. If the abnormality persists or worsens, clinical and laboratory monitoring should be initiated by the investigator and in consultation with the study medical monitor. Monitoring of ALT, AST, alkaline phosphatase, and total bilirubin should continue until levels normalize or return to approximate baseline levels.

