9.4.3.1.1. Hepatic Safety Data Collection

Additional safety data should be collected via the eCRF if 1 or more of the following conditions occur:

- elevation of serum ALT to $\geq 5 \times \text{ULN}$ on 2 or more consecutive blood tests
- elevated serum total bilirubin to $\geq 2 \times \text{ULN}$ (except for cases of known Gilbert's syndrome)

- elevation of serum alkaline phosphatase to $\geq 2 \times \text{ULN}$ on 2 or more consecutive blood tests
- patient discontinued from treatment due to a hepatic event or abnormality of liver tests
- hepatic event considered to be a SAE

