6.9.3. Planned Exploratory Analyses

Some of the planned exploratory analyses are described in Section 6.1. The remaining exploratory analyses are described in this section.

The analyses of proportions of patients reaching each target: HbA1c target $\leq 6.5\%$, body weight loss $\geq 5\%$, and body weight loss $\geq 10\%$ will employ the logistic regression model described in Section 6.1. The model for body weight target will be changed by replacing baseline HbA1c with baseline body weight as a covariate along with baseline HbA1c strata as a fixed effect. HbA1c target of the below 2 composite endpoints using LOCF will only apply a logistic regression model with an additional covariate of baseline body weight.

- HbA1c <7.0%, no body weight gain, and no documented symptomatic or severe hypoglycemia
- HbA1c <7.0%, body weight loss $\geq 5\%$, and no documented symptomatic or severe hypoglycemia

Longitudinal continuous variables (up to 52 weeks) such as HbA1c, body weight, FSG, and calcitonin will be analyzed using the MMRM described in Section 6.1. If the normality assumption is violated, an appropriate data transformation may be applied prior to analysis.

Nonlongitudinal continuous variables (up to 36 weeks) such as 6-point SMPG, C-peptide, fasting insulin, fasting glucagon, HOMA2-IR, and HOMA2-%B will be analyzed using LOCF by fitting a linear model with pooled country, treatment, and baseline HbA1c strata as fixed effects, and the corresponding baseline value as a covariate. A data transformation may be applied if data are not normally distributed.

The 6-point SMPG consists of measurements before and 2 hours after each of 3 meals within the same day. Each of the time points of the 6-point SMPG, mean of the premeal values, mean of the postmeal values, mean of all 6 time points, breakfast excursion, mid-day excursion, dinner excursion, and mean of all 3 excursions for each scheduled postrandomization visit will be summarized separately.

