A summary report and analysis for treatment-emergent abnormal laboratory values (outside the reference ranges as appropriate) will be provided for each continuous analyte by treatment. Shift tables of the change from baseline value to the maximum postbaseline value to endpoint for selected analytes using clinically meaningful thresholds will be summarized descriptively. A shift table for alanine aminotransferase, aspartate aminotransferase, alkaline phosphatase, total bilirubin level, and direct bilirubin will be generated using the following cutoffs: $\leq 1 \times \text{ULN}$, ($> 1 \times \text{ULN}$ and $< 3 \times \text{ULN}$), ($\geq 3 \times \text{ULN}$ and $< 5 \times \text{ULN}$), ($\geq 5 \times \text{ULN}$ and $< 8 \times \text{ULN}$), and $\geq 8 \times \text{ULN}$.

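### The SAP's liver shift table has no edge between 1× and 3×ULN, so it does not show the protocol's 2×ULN total bilirubin and 2× and 2.5×ULN ALP levels, and no planned output counts the protocol's joint liver criteria by arm

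*SAP*

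**What the plan says.** SAP 6.10.4 specifies the liver display: "A shift table for alanine aminotransferase, aspartate aminotransferase, alkaline phosphatase, total bilirubin level, and direct bilirubin will be generated using the following cutoffs". The bins are: up to 1×, above 1× to below 3×, 3× to below 5×, 5× to below 8×, and 8×ULN or more. The same bins serve every analyte named.

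The protocol states its liver levels in three places:

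- Section 9.4.3.1 (repeat testing within 3 to 5 days) uses ALT at 3×ULN or more, and "alkaline phosphatase $\geq 2 \times \text{ULN}$, or elevated total bilirubin $\geq 2 \times \text{ULN}$, liver testing".
- Section 9.4.3.1.1 (additional hepatic data on the eCRF) includes "elevated serum total bilirubin to $\geq 2 \times \text{ULN" and "elevation of serum alkaline phosphatase to $\geq 2 \times \text{ULN}$ on 2 or more consecutive blood tests", besides ALT at 5×ULN or more on consecutive tests.
- Section 8.1.1 (findings that prompt consideration of stopping study drug) includes "ALT or AST $>3 \times \text{ULN}$ and total bilirubin level $>2 \times \text{ULN", with prothrombin time above 1.5×ULN as an alternative to the bilirubin limb. It also lists ALP above 2.5×ULN with total bilirubin above 2×ULN, ALP above 2.5×ULN with symptoms, and ALP above 3×ULN alone.

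The other laboratory output in SAP 6.10.4 is a ranked change-from-baseline analysis, a per-analyte summary of values outside the reference range, and shift tables for unnamed analytes at thresholds left to judgement. SAP 6.1 limits summary tables to scheduled visits unless otherwise stated.

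**The concern.** The edges at 3, 5 and 8×ULN match the protocol's aminotransferase levels. Applied to bilirubin, they put a value of 1.1×ULN and one of 2.9×ULN in the same cell, although the protocol treats 2×ULN as the point at which something happens. The criteria that combine two analytes have no table at all.

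The trial exists to compare 3.0 mg and 4.5 mg with 1.5 mg, and Protocol 9.4.3 names liver safety among three areas with specific monitoring. The prespecified tables would not let a reader compare arms at the protocol's own bilirubin level, at its lower ALP levels, or on the joint criteria.

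**Working it through.** The plan states no figure to reproduce here. The check is whether each protocol level can be seen in the SAP bins. A level counts as shown if values just below and just above it fall in different bins.

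| Protocol section | Level (×ULN) | Bin just below | Bin just above | Shown? |
|---|---|---|---|---|
| 9.4.3.1 | ALT ≥3 | >1 to <3 | 3 to <5 | yes |
| 9.4.3.1 | ALP ≥2 | >1 to <3 | >1 to <3 | no |
| 9.4.3.1 | Total bilirubin ≥2 | >1 to <3 | >1 to <3 | no |
| 9.4.3.1.1 | ALT ≥5 | 3 to <5 | 5 to <8 | yes |
| 9.4.3.1.1 | Total bilirubin ≥2 | >1 to <3 | >1 to <3 | no |
| 9.4.3.1.1 | ALP ≥2 | >1 to <3 | >1 to <3 | no |
| 8.1.1 | ALT or AST >8 | 5 to <8 | ≥8 | yes* |
| 8.1.1 | ALT or AST >5 | 3 to <5 | 5 to <8 | yes* |
| 8.1.1 | ALT or AST >3 (in combination) | >1 to <3 | 3 to <5 | yes* |
| 8.1.1 | Total bilirubin >2 (in combination) | >1 to <3 | >1 to <3 | no |
| 8.1.1 | ALP >3 | >1 to <3 | 3 to <5 | yes* |
| 8.1.1 | ALP >2.5 (in combination) | >1 to <3 | >1 to <3 | no |

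*Apart from a value exactly on the edge, because the SAP bins include their lower limit and these criteria do not.

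Result: 6 of 12 entries are shown. By analyte this is ALT/AST 5 of 5, ALP 1 of 4, total bilirubin 0 of 3 (5 + 4 + 3 = 12). The table shows levels only; persistence and consecutive-test conditions are outside it.

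**Joint criteria.** Suppose an arm of n patients has a at the first level and b at the second. The number with both lies between max(0, a + b − n) and min(a, b). The counts below are illustrative assumptions, with n = 600 from the sample-size section:

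- a = 6, b = 6: from max(0, 12 − 600) = 0 to min(6, 6) = 6.
- a = 10, b = 4: from max(0, 14 − 600) = 0 to min(10, 4) = 4.

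Single-analyte counts therefore leave the joint count open. Here b is not available either, since 2×ULN is not an edge. The exception is a = 0: if no patient in the arm reaches the ALT/AST level, the joint count is 0. For zero cases in 600 the one-sided 95% upper limit is 1 − 0.05^(1/600) = 0.00498, about 0.5%, in line with 3/600. If only the planned 510 Week 36 completers contribute a sample, it is about 3/510 = 0.6%.

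**With the edges added.** Using 1, 2, 3, 5, 8 for bilirubin and 1, 2, 2.5, 3, 5, 8 for ALP, all 12 entries are shown, subject to the same on-the-edge point. The joint criteria still need their own table, because extra edges on separate tables do not give the overlap.

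**Which samples enter.** The Schedule of Activities places the chemistry panel after randomization at Weeks 36 and 52, early termination and Week 56 only. The repeat tests under Protocol 9.4.3.1 fall between visits, so the scheduled-visit rule in SAP 6.1 would leave them out by default.

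**The case against.** The strongest reply is that nothing obliges display bins to equal management levels. Protocol 10.3.4.5 promises shift tables at clinically relevant thresholds for selected analytes, and the SAP breaks no commitment. Liver is neither a listed endpoint nor in the SAP's list of events of special interest. The unnamed-analyte shift tables and the general allowance for additional analyses in SAP 6.1 leave room for the missing output. Liver findings also have other routes: repeat testing, the hepatic eCRF, AE reporting where a diagnosis results, the sponsor's review of trends, and the DMC.

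Much of this stands. It makes the point one of reporting and limits its weight. It does not remove it. For these five analytes the SAP does name cut-offs, so the general wording is not what will be programmed. It commits to no summary of the hepatic eCRF data. Protocol 8.1.1 asks only that stopping be considered for liver tests, so discontinuation tables are no substitute. SAP 6.13.1 has the DMC analyses follow the SAP; the charter, which might add to them, is not available here. For pancreatic enzymes the SAP does use the protocol's own 3×ULN level.

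Some stronger readings are tempting but unsupported:

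- A reader might infer that the 3×ULN edge is foreign to ALP. It is not: ALP above 3×ULN is a stand-alone criterion in Protocol 8.1.1, and 2.5×ULN applies only in combination.
- SAP 6.9.3 says "Longitudinal continuous variables (up to 52 weeks) such as HbA1c, body weight, FSG, and calcitonin will be analyzed using the MMRM", in a section where data after rescue or discontinuation are censored. A reader might infer that calcitonin is analysed only there. The ranked-change and reference-range summaries in SAP 6.10.4 cover continuous analytes too, and SAP 6.2 keeps post-rescue data in safety analyses. What is absent is a count at the levels in Protocol 9.2.2.4, such as a rise of 50% or more "AND an absolute value ≥ 35 ng/L at a postrandomization visit".
- The lowest eGFR bin, below 30 mL/min/1.73 m², might seem to hide the level of 15. Under Protocol 8.1.1 a confirmed value below 15 requires permanent discontinuation of study drug, and SAP 6.3 summarizes reasons for discontinuation by arm.

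**Conclusion.** The point holds for the liver tables. The planned bins show 6 of the protocol's 12 single-analyte liver entries and none of the three total bilirubin entries. No specified output counts the joint criteria by arm. The analytes are measured and the extra hepatic data are collected, so only the prespecified presentation is deficient. The primary and secondary efficacy results are unaffected.

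A reader might go further and conclude that a liver signal would pass unnoticed, or that the 0.5% bound for zero joint cases could never be stated. The documents support neither. The other routes for liver findings remain open, and the bound follows whenever an arm has no patient at the ALT/AST level. The tables generally cannot settle the joint count once some patients reach that level.

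The conclusion assumes that the tables are programmed as SAP 6.10.4 is written, and that neither the DMC charter nor an undocumented shell already supplies these counts. It is a change worth making, because it is nearly free and concerns the comparison between doses.

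**What to change.** In SAP 6.10.4:

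- Add a 2×ULN edge for bilirubin. The protocol gives a level for total bilirubin only; direct bilirubin can share the edge for display.
- Add 2× and 2.5×ULN edges for ALP. Keep the ALT and AST bins.
- Add one patient-level table by arm in the Safety Population. It should count ALT or AST above 3×ULN with total bilirubin above 2×ULN (or prothrombin time above 1.5×ULN where measured), and ALP above 2.5×ULN with total bilirubin above 2×ULN. Use the strict inequalities of Protocol 8.1.1. Say whether the two findings must come from the same sample.
- State that unscheduled and repeat liver tests enter the maximum postbaseline value, as an exception to the scheduled-visit rule in SAP 6.1.

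Optional and minor: an edge at 15 mL/min/1.73 m² in the eGFR shift table of SAP 6.10.1.2.9, and by-arm counts of calcitonin at the levels in Protocol 9.2.2.4.

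The cost is SAP wording, a few more table shells and some sparse cells. No new data are needed. These are display thresholds taken from the protocol as it stands; no clinical rule changes.

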6.10.5. Immunogenicity

Summaries of incidence of dulaglutide anti-drug antibodies (ADA) will be generated for treatment-emergent ADA by treatment through Week 36 (Visit 9) and through Week 56 (Visit 12).

6.11. Health Outcomes/Quality-of-Life Analyses

All parameters will be analyzed using on-treatment without rescue (Section 6.1).

6.11.1. Diabetes Injection Device Experience Questionnaire

Each item in the Diabetes Injection Device Experience Questionnaire will be summarized descriptively by treatment using LOCF at Week 12. Similarly, the device characteristic subscale and 3 global item scores (satisfaction, ease of use, and convenience) will be summarized descriptively by treatment. These items will also be analyzed using linear model with pooled country, baseline HbA1c strata, and treatment as fixed effects.

6.11.2. European Quality of Life 5-Dimension 5 Level

Each item will be summarized descriptively by treatment at each scheduled visit at which the European Quality of Life 5–Dimension 5 Level (EQ-5D-5L) questionnaire is administered. The changes from baseline in the index and visual analog scale scores will be analyzed using MMRM with pooled country, baseline HbA1c strata, treatment, visit, and treatment-by-visit interaction as fixed effects, and corresponding baseline as a covariate.

6.11.3. Impact of Weight on Self-Perceptions Questionnaire

Descriptive summaries by treatment at each scheduled visit at which the Impact of Weight on Self-Perceptions Questionnaire (IW-SP) is administered will be presented for each item. The changes from baseline in IW-SP total and transformed scores will be analyzed using an MMRM with pooled country, baseline HbA1c strata, treatment, visit, and treatment-by-visit interaction as fixed effects, and corresponding baseline as a covariate.

6.11.4. Ability to Perform Physical Activities of Daily Living

Descriptive summaries by treatment at each scheduled visit at which the Ability to Perform Physical Activities of Daily Living (APPADL) is administered will be presented for each item. The changes from baseline in APPADL total and transformed scores will be analyzed using an MMRM with pooled country, baseline HbA1c strata, treatment, visit, and treatment-by-visit interaction as fixed effects, and corresponding baseline as a covariate.

6.12. Subgroup Analyses

Subgroup analyses of the treatment interaction for important factors, including age group (<65 years, ≥65), race, gender, country, duration of diabetes (<median, ≥median), baseline HbA1c (<8.5%, ≥8.5%), body weight (<median, ≥median), and body mass index (<median, ≥median), may be conducted for the primary endpoint of HbA1c. Country will use the pooled country.

These analyses will be conducted using the MMRM with treatment, visit, subgroup, treatment-by-visit, treatment-by-subgroup, visit-by-subgroup, and treatment-by-visit-by-subgroup as fixed effects, and baseline as a covariate. If the MMRM fails to converge, the corresponding ANCOVA or ANOVA model (LOCF) will be used.

When analyzing baseline HbA1c as a subgroup, the baseline HbA1c will not be included as a covariate to avoid colinearity.

Treatment-emergent AEs occurring in >5% of patients will be summarized descriptively for the patients with the top quartile of body weight reduction from baseline by treatment group.

Other exploratory subgroup analyses may be performed as deemed appropriate.

6.13. Interim Analyses and Data Monitoring Committee

No interim analyses of efficacy are planned for this study.

An independent Data Monitoring Committee (DMC) will review unblinded interim analysis results in order to monitor the safety of the patients in the study until the last patient completes the Week 36 visit (Visit 9). The detailed analysis and communication plan for the interim analyses will be defined in a separate DMC charter. An internal Statistical Analysis Center external to the study team will perform the data analyses for the DMC. As no efficacy analyses are planned for the DMC, the family-wise error rate will not be affected by any of these analyses; hence, no alpha spending is necessary.

Study sites may receive information about interim results ONLY if these results may have an impact on the safety of patients in this trial.

The timing for DMC is described in GBGL Protocol Section 10.3.8.

Appendix 1.

Summary of the Data and Primary Analysis for the Primary and Secondary Efficacy Endpoints by Type of Estimand

	Efficacy Estimand	Treatment-Regimen Estimand
Data		
Data Included in the Analyses	
 All patients in the ITT population with a baseline value and at least 1 postbaseline value for the measure of interest are included. Values are excluded after treatment discontinuation or start of antihyperglycemic medications lasting >14 days. 	
 All patients in the ITT population with a baseline value for the measure of interest are included.
Primary Analysis for Each Endpoint		
Primary Endpoint: Change from baseline in HbA1c at Week 36	
 MMRM with effects for treatment, pooled country, visit, treatment-by-visit interaction, and baseline HbA1c as a covariate, 	
 If the Week 36 value is missing, multiple imputation will be used to impute a value such that the reference group includes patients from the same treatment group and same treatment discontinuation status (yes, no) who had a value at Week 36. ANCOVA with effects for treatment, pooled country, and baseline HbA1c as a covariate.
Secondary Endpoint: Change from baseline in body weight at Week 36	
 MMRM with effects for treatment, pooled country, baseline HbA1c stratum (<8.5%, ≥8.5%), visit, treatment-by-visit interaction, and baseline body weight as a covariate. 	
 If the Week 36 value is missing, multiple imputation will be used to impute a value such that the reference group includes patients from the same treatment group and same treatment discontinuation status (yes, no) who had a value at Week 36. ANCOVA with effects for treatment, pooled country, baseline HbA1c stratum (<8.5%, ≥8.5%), and baseline body weight as a covariate.

Summary of the Data and Primary Analysis for the Primary and Secondary Efficacy Endpoints by Type of Estimand

	Efficacy Estimand	Treatment-Regimen Estimand
Primary Analysis for Each Endpoint		
Secondary Endpoint: Change from baseline in fasting serum glucose (FSG) at Week 36	
 MMRM with effects for treatment, pooled country, baseline HbA1c stratum (<8.5%, ≥8.5%), visit, treatment-by-visit interaction, and baseline FSG as a covariate. 	
 If the Week 36 value is missing, multiple imputation will be used to impute a value such that the reference group includes patients from the same treatment group and same treatment discontinuation status (yes, no) who had a value at Week 36. ANCOVA with effects for treatment, pooled country, baseline HbA1c stratum (<8.5%, ≥8.5%), and baseline FSG as a covariate.
Secondary Endpoint: Achieving HbA1c goal <7% at Week 36	
 Longitudinal logistic regression with effects for treatment, pooled country, visit, treatment-by-visit interaction, and baseline HbA1c as a covariate. 	
 If the Week 36 value is missing, the patient will be considered as not having met the goal. Logistic regression with effects for treatment, pooled country, and baseline HbA1c as a covariate.

Abbreviations: ANCOVA = analysis of covariance; HbA1c = glycated hemoglobin A1c; ITT = intent to treat; MMRM = mixed-model repeated measure.

Leo Document ID = 9a56661a-0d45-4976-9782-d6580268a5bb

Approver: [REDACTED]
Approval Date & Time: 06-Jun-2019 21:14:40 GMT
Signature meaning: Approved
